7.3. Overview of Planned Adverse Events of Special Interest

Table 10 provides an overview of the planned Adverse Event analyses, with full details of data displays being presented in Appendix 12: List of Data Displays.

Table 10 Overview of Planned Adverse Events of Special Interest

Endpoint		Absolute	
	Summary	Individual	
	Т	L	
Adverse Events of Special Interest (AESI)			
Overall AESI by Category	Υ	Υ [1]	
Malignant Neoplasm AESI by Category & PT	Υ		
Post-Infusion Systemic Reaction AESI by Category & PT	Υ		
Serious Post-Infusion Systemic Reaction AESI by Category & PT	Υ		
Infection AESI by Category & PT	Υ		
Serious Infection AESI by Category & PT	Υ		
Infection AESI Leading to PD Discontinuation of Study Drug or WD from Study by Category & PT	Υ		
Depression/Suicide/Self-injury AESI by Category & PT	Υ		
Deaths by Category & PT	Υ		
Adverse Events of Special Interest (AESI) Rates			
Overall AESI Rates by Category	Υ		
Malignant Neoplasm AESI Rates by Category & PT	Υ		
Post-Infusion Systemic Reaction AESI Rates by Category & PT	Υ		
Serious Post-Infusion Systemic Reaction AESI Rates by Category & PT	Υ		
Infection AESI Rates by Category & PT	Υ		
Serious Infection AESI Rates by Category & PT	Υ		
Infection AESI Leading to PD Discontinuation of Study Drug or WD from Study Rates by Category & PT	Y		
Depression/Suicide/Self-injury AESI Rates by Category & PT	Υ		

NOTES:

- T = Table, L = Listing, Y = Yes display generated, (xN) = Number of separate displays generated.
- Summary = Represents TFL related to any summaries (i.e. descriptive statistics) of the observed raw data.
- Individual = Represents FL related to any displays of individual subject observed raw data.
- [1] Listing generated by AESI Category, SOC, PT and Verbatim Term.

7.3.1. Adverse Events of Special Interest

AESI have already been identified by the GSK Safety Review Team (SRT). This information will be provided for analysis purposes via an adjudication spreadsheet, and therefore, does not need to be re-derived from the raw data. For a broader description, see Appendix 10: PSAP Sections for AESI Reporting.

The reporting of AESIs is defined below.

An overall summary of the incidence of AESI will be tabulated, and presented by study year and "any time post-baseline". Rate of events per 100 person-years will also be reported. Further summaries of the preferred terms assigned to each AE special interest category will be provided.

A listing of all AESIs will be produced.

The categorizations for the adverse events of special interest groups are:

Malignant Neoplasms

- Malignancies Excluding non-melanoma skin cancer (NMSC)
- Malignancies Including NMSC
 - Solid Tumour
 - Hematologic
 - Skin (All)
 - NMSC
 - Excluding NMSC
- Tumours of unspecified malignancy adjudicated as malignant per GSK

Post-Infusion Systemic Reactions (PISR)

- PISR per Anaphylactic Reaction Customized MedDRA Query (CMQ) narrow search
- PISR per Anaphylactic Reaction CMQ broad search
- PISR per Anaphylactic Reaction CMQ algorithmic search
- Serious Anaphylaxis per Sampson Criteria per GSK adjudication
- Serious Acute PISR/Hypersensitivity per GSK adjudication
 - Serious Acute PISR Excluding Hypersensitivity per GSK adjudication
 - Serious Acute Hypersensitivity Reactions per GSK adjudication
- Serious Delayed Acute Hypersensitivity Reactions per GSK adjudication
- Serious Delayed Non-Acute Hypersensitivity Reactions per GSK adjudication

All Infections of Special Interest (All and Serious, separately)

- All opportunistic infections (OI) per GSK adjudication
- OI per GSK adjudication excluding Tuberculosis and Herpes Zoster
- Active Tuberculosis
 - Non-Opportunistic
 - Opportunistic
- Herpes Zoster
 - Non-Opportunistic
 - Opportunistic
 - Recurrent
 - Disseminated
- Sepsis

Depression*/suicide/self-injury (All and Serious, separately)

- Depression* (excluding suicide and self-injury)
- Suicide/self-injury
- Serious suicide/self-injury per GSK adjudication
 - Suicidal Behaviour
 - Completed Suicide
 - Suicidal Ideation

Self-injurious Behaviour without Suicidal Intent

Deaths

7.4. Overview of Planned Laboratory, Immunogenicity and Vital Signs Summaries

Table 11 provides an overview of the planned Laboratory, Immunogenicity, Immunoglobulins and Vital Signs summaries by parent randomised treatment group, with further details of data displays being presented in Appendix 12: List of Data Displays.

Table 11 Overview of Planned Laboratory, Immunogenicity and Vital Signs

	Sumr	Individual	
	Т	F	L
Laboratory Parameters (by Visit)			
Lab Parameters Visit Values	Y (x5) [1] [2]	Y (x5) [1]	Y (x6) [3]
Lab Parameter Change from BL	Y (x5) [1] [2]	Y (x5) [1]	
Worst Laboratory Toxicity Grade (by Year Interval)			
Worst Lab Toxicity Grade	Y (x6) [3]		
Worst Lab Toxicity Grade by At least 2 Grades from BL	Y (x6) [3]		
Grade 3 & 4 Lab Toxicity Results			Y (x6) [3]
Laboratory Reference Range Shifts			
Lab Reference Shifts from BL	Y (x6) [3]		
Hepatobiliary (Liver)			
Liver Events			Y (x3) [4]
Immunogenicity			
Immunogenicity Response by Visit	Y		Υ
Immunogenicity Response by Year Interval	Y		
Vital Signs			
Vital Signs Visit Values	Y		Υ
Pregnancies			
On-study Pregnancies per End of Treatment CRF			Υ

NOTES:

- BL = Baseline, T = Table, F = Figure, L = Listing, Y = Yes display generated, (xN) = Number of separate displays generated
- Summary = Represents TFL related to any summaries (i.e. descriptive statistics) of the observed raw data.
- Individual = Represents FL related to any displays of individual subject observed raw data.
- [1] Separate displays generated for [A] Haematology, [B] Liver Function, [C] Electrolytes, [D] Other Chemistries, [E] Immunoglobulins.
- [2] A combined display will be generated for Absolute and Change from baseline for each laboratory parameter.
- [3] Separate displays generated for [A] Haematology, [B] Liver Function, [C] Electrolytes, [D] Other Chemistries, [E] Urinalysis, [F] Immunoglobulins. Note: immunoglobulin data will be summarised separately by parent study. See Section 5.1.
- [4] Separate displays generated for [A] Liver Assessment, [B] Liver Biopsy Details, [C] Liver Imaging.

^{*} Including mood disorders and anxiety.

7.4.1. Clinical Laboratory Evaluations

- Laboratory parameters which are continuous numeric values will be analyzed using summary statistics, and those with categorical results will be summarized using frequencies and percentages.
- Analyses will be performed based on the observed data. Only central laboratory data will be summarized.
- Refer to Appendix 5: Derived and Transformed Data for handling of laboratory values that are above or below the lower limit of quantification.
- Listings will be generated for all laboratory results, and additionally for Grade 3 or Grade 4 laboratory toxicity results.
- Baseline is defined as described in Section 11.4.2 and a list of laboratory parameters collected and definition of the toxicity grades provided in Appendix 9: Laboratory Parameters & Adverse Events Grading Tables.
 - Note: UREA is collected in BEL114333/BEL113750 and BUN is collected in BEL112341. "Urea (mmol/L) & BUN (mmol/L)" will be displayed as a single parameter in tabular summaries of laboratory parameters and a footnote added to highlight that different tests were performed in the different studies.
 - Note: Bilirubin direct data were not collected during the parent study for BEL112341 subjects; thus, because of missing data at baseline and postbaseline visits for the first 6 months of belimumab treatment (and data for the subsequent 12 months is limited to the placebo group), these subjects will be excluded from this summary.
- Toxicities will be reported as derived by the GSK EDU, as protocol toxicity grading was applied (or as assigned programmatically in the ADaM dataset creation, for lymphocytes, spot urine protein creatinine ratio and urine RBC). Note: toxicity data for partial thromboplastin time and prothrombin time will not be summarised because the data were only collected in the parent study. However, PT/PTT at baseline will be displayed in tabular summaries of laboratory parameters (see Section 7.4.2).

Additionally, for potassium, glucose, calcium and sodium, toxicities are bi-directional (i.e. high or low directions) and both will be summarised by name of the toxicity.

- Potassium: hypokalemia, hyperkalemia
- Glucose: hypoglycemia, hyperglycemia
- Calcium: hypocalcemia, hypercalcemia
- Sodium: hyponatremia, hypernatremia

For example, calcium will have two toxicity sections, one for hypocalcemia and one for hypercalcemia and mapped to their high or low as

- RESULT < (LLN+ULN)/2 = "Hypo" toxicity
- RESULT > (LLN+ULN)/2 = "Hyper" toxicity.

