3.2. Discussion of Design

The BEL113750 study design was based on 2 global, Phase III clinical trials (HGS1006-C1057 and HGS1006-C1056) which demonstrated that subjects treated with belimumab had a statistically significantly better response rate at the primary endpoint at week 52, than those treated with placebo. BEL114333 provides subjects who complete the BEL113750 study the option of continuing treatment with belimumab for those randomized to belimumab, or the option to begin treatment with belimumab for those

randomized to placebo, as an add-on to their standard of care SLE therapy. Subjects who completed 48 weeks of treatment and return for the final 52-week evaluation on BEL113750 may be recruited into this continuation protocol of open-label belimumab. BEL114333 provides subjects who complete the open-label SC extension of C1115 in Japan the option of continuing treatment with IV belimumab, as an add-on to their standard of care SLE therapy.

This study will continue until the subject withdraws from the trial, or intravenous belimumab becomes commercially available in the relevant participating country, or the subject elects to participate in another belimumab continuation study for SLE, or upon the decision by the sponsor to discontinue development/marketing of belimumab for SLE.

In the Phase II and Phase III continuation trials, the incidence rates of adverse events (AEs) in general and by SOCs (including infections), serious AEs, and malignancies were comparable to placebo per 100 subject years of exposure. The overall incidence rate of adverse events remained stable or decreased over 6 years of exposure to belimumab. GlaxoSmithKline (GSK) will remain blinded to subjects' treatment until all data from the Phase III study, BEL113750, are locked and unblinded. Clinical sites will remain blinded to previous treatment on BEL113750 until after the results of BEL113750 are publicly disclosed.

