6.1.1. Procedures (Day 0)

6.1.1.1. Subjects in BEL113750

The Week 52 visit in BEL113750 will serve as the Day 0 visit for Protocol BEL114333. The subject must sign the informed consent for this protocol between the Week 48 and Week 52 visits of the BEL113750 study prior to any procedure in this protocol (that is not present in the BEL113750 protocol) being performed. On Day 0 of this study, a subject will be reassessed for Inclusion/Exclusion criteria of the BEL114333 study and receive belimumab, after completing the Week 52 procedures from the BEL113750 study. Site personnel will access the IVRS to enrol the subject in the study.

Procedures necessary for this protocol and for the prior Phase III protocol (BEL113750) need only be performed once. The results of any Day 0 procedure in this protocol which are also part of the BEL113750 protocol should be recorded on the BEL113750 eCRF. Only the additional procedures required for this protocol will be recorded in the BEL114333 protocol eCRF. The relevant Week 52 eCRF data will be transferred to the Day 0 BEL114333 eCRF.

The following assessments will be performed as part of the Week 52 assessment on BEL113750 and need only be performed once as described above.

- Urine for pregnancy testing- for all women with an intact uterus, unless exempted from pregnancy testing (i.e., of non-childbearing potential - women who had a hysterectomy, are post-menopausal which is defined as 1 year without menses, have both ovaries surgically removed or have current documented female sterilization procedure).
- Record of Concurrent Medications.

- Adverse Events.
- Physical exam
- Vital signs (Systolic and diastolic blood pressure (sitting), heart rate, and oral temperature will be measured. See Section 6.3.11).
- Blood samples for: (see [Appendix 5](#)– Laboratory Tests):
 - Haematology.
 - Modified Chem 20 (non-fasting). (CPK MUST be done for subjects with myositis in order to score SELENA SLEDAI/BILAG).
 - Serum Immunoglobulin isotypes (IgG, IgM, IgA).
 - Immunogenicity testing.
 - Biological markers (Complement C3 and C4)
 - Anti-dsDNA autoantibodies.
 - B-cell subsets (CD20⁺, CD20⁺/27⁺ memory, CD20⁺/27⁻ naïve, CD20⁺/69⁺ activated, CD20⁺/138⁺ plasmacytoid, CD19⁺/27^{BRIGHT}/38^{BRIGHT} SLE subset and CD20/138⁺ plasma cells) at selected sites.
- Urine sample for:
 - Routine urinalysis.
 - Spot urine for macroscopic/microscopic/proteinuria assessments.
- Disease activity scales:

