 - Physician’s Global Assessment (PGA). (See [Appendix 1](#)).
 - SELENA SLEDAI (See [Appendix 1](#); refer to Section 6.2.2.3 Guidelines for Scoring Proteinuria).
 - SLE Flare Index. (See [Appendix 1](#)).
 - BILAG. (See [Appendix 2](#)).
 - SLICC/ACR Damage Index (See [Appendix 3](#)).

The following additional procedures beyond those described above are required at Day 0 for Protocol BEL114333:

- Ensure Informed Consent Form has been signed.
- Confirm Eligibility.
- PT/PTT
- Administer belimumab.

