6.1.1.2. Subjects in C1115

The Day 168 visit of the open-label extension of C1115 will serve as the Day 0 visit for Protocol BEL114333. The subject must sign the informed consent for this protocol on or before the Day 168 visit of the open-label extension of C1115 prior to any procedure in this protocol (that is not present in the C1115 protocol) being performed. On Day 0 of this study, a subject will be reassessed for Inclusion/Exclusion criteria of the BEL114333 study and receive IV belimumab, after completing the Day 168 procedures from the C1115 study. Site personnel will access the IVRS to enrol the subject in the study.

Procedures necessary for this protocol and for the prior Phase III protocol (C1115) need only be performed once. The results of any Day 0 procedure in this protocol which are also part of the C1115 protocol should be recorded on the C1115 eCRF. Only the additional procedures required for this protocol will be recorded in the BEL114333 protocol eCRF.

The following assessments will be performed as part of the Day 168 assessment on C1115 and need only be performed once as described above and entered into the C1115 eCRF only.

- Urine for pregnancy testing- for all women with an intact uterus, unless exempted from pregnancy testing (i.e., of non-childbearing potential - women who had a hysterectomy, are post-menopausal which is defined as 1 year without menses, have both ovaries surgically removed or have current documented female sterilization procedure).
- Record of Concurrent Medications.
- Adverse Events.
- Blood samples for: (see [Appendix 5](#)– Laboratory Tests):
 - Haematology.
 - Modified Chem 20 (non-fasting). (CPK MUST be done for subjects with myositis in order to score SELENA SLEDAI/BILAG).
 - PT/PTT
 - Serum Immunoglobulin isotypes (IgG, IgM, IgA).
 - Immunogenicity testing.
 - Biological markers (Complement C3 and C4)
 - Anti-dsDNA autoantibodies.
 - B-cell subsets (CD20⁺, CD20⁺/27⁺ memory, CD20⁺/27⁻ naïve, CD20⁺/69⁺ activated, CD20⁺/138⁺ plasmacytoid, CD19⁺/27^{BRIGHT}/38^{BRIGHT} SLE subset and CD20⁺/138⁺ plasma cells) at selected sites.
- Urine sample for:
 - Routine urinalysis.

- Spot urine for macroscopic/microscopic/proteinuria assessments.
- Disease activity scales:
 - Physician's Global Assessment (PGA). (See [Appendix 1](#)).
 - SELENA SLEDAI (See [Appendix 1](#); refer to Section 6.2.2.3 Guidelines for Scoring Proteinuria).
 - SLE Flare Index. (See [Appendix 1](#)).
 - BILAG. (See [Appendix 2](#)).

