2.4.1. Treatment Comparisons

All subjects will be treated with open-label IV belimumab for the duration of the study BEL114333. The analyses will be performed on data from all subjects as one total belimumab treatment group by year of belimumab treatment.

As subjects started to receive belimumab treatment in the parent study, or the open-label extension of the parent study BEL112341, or the open-label study BEL114333, different time points to start of belimumab treatment will be used to define subject follow up in the analysis. See Figure 1.

Analyses will be based on all available follow-up from the first dose of belimumab treatment through to study end.

Additional safety (e.g., labs), efficacy and study population summaries will be presented by parent study randomised treatment groups (belimumab vs placebo); however, these comparisons will be descriptive in nature. For the remainder of the document, parent randomised treatment group will be used to refer to the treatment to which a subject was randomised in the parent study, irrespective of formulation.

Figure 1 First Belimumab Dose/Baseline Definition

Analyses will be based on all available data from the first belimumab dose through to study end, BEL114333. As subjects started to receive belimumab in the parent study, or the open-label extension of BEL112341, or the open-label study BEL114333, different timepoints to start of belimumab treatment are used in the analysis (as shown). Baseline is defined as the last available value prior to the first belimumab dose.

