5.1. General Data Considerations

- This is a multi-centre study in Japan and Korea. There are no planned adjustments made for multiple centres or regions.
- As no formal hypotheses are being tested, there are no planned adjustments for multiple comparisons or multiplicity.
- As all subjects will be treated with belimumab and there are no hypothesis tests, no additional strata or covariates will be employed in the analyses. Subgroups will be defined for further exploration of the data in a descriptive fashion.
- Reporting of data is by year of belimumab treatment beginning on the date when subjects received their first dose of belimumab, irrespective of the formulation (Section 2.4.1 and Section 11.2.1).
- Baseline is defined as the last available value prior to the initiation of treatment with belimumab and will henceforth be referred to as 'Belimumab baseline'. See Appendix 4: Data Display Standards & Handling Conventions for more details on baseline definitions.
- For summaries performed by belimumab visit, placebo subjects are aligned based on start of exposure to belimumab (see Section 11.2.2 for details of the visit mapping).
 - Note, for BEL114333, subjects randomized to belimumab in the parent study were off-set by an additional 4 weeks compared to the open-label visit schedule, in order to complete the final assessments at the parent study Week 52 visit. Therefore, the mapping was adjusted in order to align the ensuing open-label visits. This was achieved by mapping the parent study Week 52 visit to the Belimumab Visit Year 1 Week 48 (and dropping the parent study Week 48). Ongoing open-label visits will always align.

Note, for subjects ongoing in BEL114333 at the time of study end, there is one year off-set between the parent randomised treatment groups until the last dose was administered in March 2018. Data for the last year will be limited to the belimumab group.

• There is a single data base that captures both parent study (i.e. DB phase of BEL113750) and open-label data for study BEL113750. The dividing line between parent study and open-label data is determined by the Day 365 visit. Any new data after this visit is regarded as open-label.

Note, after the database was frozen for the parent study analysis (DB data), technical limitations required the entire data base to be open in order to enter open-label information. Thus, sites had the ability to also change data pertaining to the parent study.

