7.4.3. Worst laboratory toxicity grade post-baseline

• Toxicity grading for each analyte will be summarized. This reflects the worst grade for each analyte across all subjects and all assessments for each year interval and at any time post-baseline. The display will summarize the number (%) of subjects for each of the toxicity grades.

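### The SAP drops PT/PTT toxicity for a reason the Day 0 schedule contradicts for BEL113750 subjects, and which is no ground for exclusion for BEL112341 subjects

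*SAP*

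**What the plan says.** SAP 7.4.1 gives one reason for leaving PT and PTT out of the toxicity output: "toxicity data for partial thromboplastin time and prothrombin time will not be summarised because the data were only collected in the parent study". It keeps PT/PTT in the baseline laboratory tables.

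Protocol 6.1.1.1 covers subjects coming from BEL113750. It first lists what is done under that study's Week 52 visit, then introduces a second list: "The following additional procedures beyond those described above are required at Day 0 for Protocol BEL114333". PT/PTT is on the second list. On where results go, the same section says: "Only the additional procedures required for this protocol will be recorded in the BEL114333 protocol eCRF". Protocol Table 2 and the SAP's copy in 11.1.1.1 both mark PT/PTT at Day 0.

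For subjects from BEL112341, protocol 6.1.1.2 puts PT/PTT among the assessments that "will be performed as part of the Day 168 assessment on C1115 and need only be performed once".

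On scope, SAP 2.4.1 says: "Analyses will be based on all available follow-up from the first dose of belimumab treatment through to study end". SAP 7.4.3 says of the worst-grade table: "This reflects the worst grade for each analyte across all subjects and all assessments for each year interval and at any time post-baseline". Protocol 8.1.3 commits to summarising Grade 3 or 4 laboratory abnormalities and shifts of two or more grades. PT and PTT have defined grades in protocol Appendix 6 and SAP 11.9.2.

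**The concern.** Safety is the primary objective, and the SAP builds its safety analysis on time since first belimumab dose, whichever study that time was spent in. A graded laboratory parameter is removed from the toxicity tables because of where it was collected. That reason conflicts with the schedule for one parent study. For the other it appeals to a boundary that the SAP does not use elsewhere.

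The exclusion is also missing from SAP Table 1, which lists changes from the protocol's analysis plan. A reader of the study report would conclude that no PT/PTT was scheduled on belimumab within the analysis period. At stake are the on-treatment summary of two parameters and the accuracy of the stated reason. No hypothesis test or efficacy result is involved.

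**Working it through.** The plan gives no figure to reproduce. The check is a count of scheduled draws, followed by a check of where the Day 0 draw falls in the year intervals.

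**Step 1. PT/PTT in each schedule.**
- BEL113750 double-blind (SAP 11.1.2.1): screening only.
- BEL114333 Year 1 (protocol Table 2, SAP 11.1.1.1): Day 0 only. Additional years: none.
- BEL112341 double-blind (SAP 11.1.2.2.1): Day 0, Weeks 8, 24 and 52, or early exit.
- BEL112341 open-label (SAP 11.1.2.2.2): Day 168 (Week 24).

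**Step 2. Which draws are on belimumab.** Entry from BEL113750 follows a full course: "Subjects who completed 48 weeks of treatment and return for the final 52-week evaluation on BEL113750 may be recruited". So for the belimumab arm the Day 0 draw comes after 48 weeks of treatment. The SAP treats that visit as post-baseline by "mapping the parent study Week 52 visit to the Belimumab Visit Year 1 Week 48". For the BEL113750 placebo arm, Day 0 is the first belimumab dose, and SAP 11.2.2 counts values on that date as baseline. For the BEL112341 placebo arm, baseline is the double-blind Week 52 visit.

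| Origin and randomised arm | Draws after first belimumab dose | Count |
|---|---|---|
| BEL113750 belimumab | BEL114333 Day 0 | 1 |
| BEL113750 placebo | none | 0 |
| BEL112341 belimumab | Weeks 8, 24, 52; open-label Day 168 | 4 |
| BEL112341 placebo | open-label Day 168 | 1 |

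**Step 3. Total for the 25 BEL112341 subjects.** If b of them were randomised to belimumab, the scheduled total is 4b + (25 − b) = 25 + 3b. The split is not given, so with b from 0 to 25 the range is 25 to 100 draws. No total can be formed for BEL113750, because the number of belimumab-randomised Japan and Korea subjects is not given.

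**Step 4. Consistency with the baseline promise.** Under SAP 11.4.2, baseline for the BEL113750 placebo arm reaches back no further than double-blind Week 48. The screening PT/PTT lies outside that window. The only scheduled PT/PTT inside it is BEL114333 Day 0. If PT/PTT had been collected only in the parent study, these subjects would have no baseline value to display.

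**Step 5. Can a shift be derived?** Yes. For the BEL113750 belimumab arm, SAP 11.4.2 accepts a screening value when a test was scheduled only at screening. For BEL112341, Day 0 (belimumab arm) or Week 52 (placebo arm) serves.

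**Step 6. Year placement of the BEL113750 value.** The SAP numbers the first dose as Day 1, so protocol Day 364 is SAP Day 365, the last day of Year 0-1. The first BEL114333 dose may fall 2 to 8 weeks after the last parent-study dose, nominally Day 336. That gives protocol Days 336 + 14 = 350 to 336 + 56 = 392, or SAP Days 351 to 393. Year 1-2 starts on Day 366, so the same visit can land in either year by scheduling alone.

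**The case against.** The strongest reply is that the sentence is loose rather than wrong in effect. No PT/PTT is scheduled after Day 0. SAP 5.1 draws the line between parent and open-label data at the Day 365 visit, so a draw at the shared Week 52/Day 0 visit could be called parent-side. For the 25 BEL112341 subjects the sentence is correct. The values are not lost: SAP 7.4.1 plans listings of all laboratory results and of Grade 3 or 4 results, and protocol 6.3.3 has clinically significant abnormalities recorded as adverse events. Omitting sparse parameters has a precedent in the SAP's handling of direct bilirubin for BEL112341 subjects.

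Much of this stands, and it limits the point. It does not rescue the reason. Protocol 6.1.1.1 places PT/PTT outside the Week 52 procedures and in the BEL114333 eCRF. Even if the draw is labelled parent-side, it lies inside the SAP's analysis period. For direct bilirubin the SAP gives missing data as its reason; for PT/PTT it does not plead sparseness. The objection also defeats a by-year table, as step 6 shows.

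A reader might infer that on-belimumab PT/PTT results are known to exist for most subjects. The documents show schedules, not results, and do not give the arm sizes. A reader might also infer that a coagulation problem is being hidden. Nothing in either document suggests one, and coagulation is not among the adverse events of special interest.

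**Conclusion.** The stated reason needs correcting. It is contradicted by the schedule for BEL113750 subjects. It is accurate for the 25 BEL112341 subjects, but is not a valid ground given the SAP's own analysis period. By schedule, every belimumab-randomised completer has at least one on-belimumab PT/PTT draw: exactly one from BEL113750 and four from BEL112341.

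The point is minor. The data are sparse, the listings remain, and no conclusion is shown to change. The verdict assumes that visits were completed as scheduled. If the Day 0 draw was not made, the BEL113750 count falls to zero. The SAP's omission would then have a different, unstated cause, and only the BEL112341 values would remain to summarise.

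**What to change.** 1. Replace the reason in SAP 7.4.1 with an accurate one: PT/PTT was scheduled at BEL114333 Day 0 for subjects from BEL113750, and on belimumab during BEL112341.
2. Add PT and PTT to Table 2.62 (worst grade, haematology) and Table 2.68 (worsening of at least two grades, haematology), in the column for any time post-baseline only. Show n as the number of subjects with a value after the first belimumab dose. Leave out the year intervals, for the reason in step 6.
3. If the Day 0 PT/PTT was not obtained, say so and report it as a departure from the protocol.

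The cost is two parameters in existing tables, using grades already defined in SAP 11.9.2. If the data transfer carries no grade for them, it can be assigned in programming, as the SAP already does for lymphocytes. The drawback is small denominators and, for BEL113750 subjects, a worst grade that rests on a single value; a footnote should say so. The listings need no change.
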